3.2. Secondary Endpoints

The secondary endpoints are:

- Incidence and severity of adverse events (AEs) and incidence of abnormalities in laboratory safety assessments, 12-lead electrocardiograms (ECGs), vital signs measurements, and physical examinations.

4. STUDY DESIGN

This study will be an open-label, randomized, three-period, six-sequence crossover study of GDC-9545 administered at 30 mg in healthy females of non-childbearing potential to determine the relative bioavailability of the Phase 3 capsule formulation to the Phase 1 tablet formulation in the fasted state and the effect of food on the Phase 3 capsule formulation. Eighteen subjects will be enrolled in the study at a single study site to complete a minimum of 12 subjects. Study treatments are as follows:

Treatment A: 30-mg dose of GDC-9545 (three 10-mg tablets) administered orally with approximately 240 mL room temperature water after at least an 8-hour fast.

Treatment B: 30-mg dose of GDC-9545 (one 30-mg capsule) administered orally with approximately 240 mL room temperature water after at least an 8-hour fast.

Treatment C: 30-mg dose of GDC-9545 (one 30-mg capsule) administered orally with approximately 240 mL room temperature water within 30 minutes of eating a high-fat meal.

A summary of the sequences is presented in Table 1.

[figure not shown]
Table 1: Three-Period, Six-Sequence Crossover Study Design

Sequence	Number of Subjects	Period 1 ^a	Period 2 ^a	Period 3 ^a
I	3	Treatment A	Treatment B	Treatment C
II	3	Treatment B	Treatment C	Treatment A
III	3	Treatment C	Treatment A	Treatment B
IV	3	Treatment A	Treatment C	Treatment B
V	3	Treatment B	Treatment A	Treatment C
VI	3	Treatment C	Treatment B	Treatment A

^a A minimum of 10 days between doses, with 7-day pharmacokinetic collection postdose and washout.
 Treatment A: 30-mg dose of GDC-9545 (three 10-mg tablets) administered orally with approximately 240 mL room temperature water after at least an 8-hour fast.
 Treatment B: 30-mg dose of GDC-9545 (one 30-mg capsule) administered orally with approximately 240 mL room temperature water after at least an 8-hour fast.
 Treatment C: 30-mg dose of GDC-9545 (one 30-mg capsule) administered orally with approximately 240 mL room temperature water within 30 minutes of eating a high-fat meal.

A schematic of the study design is presented in Figure 1.

Figure 1: Study Design

Potential subjects will be screened to assess their eligibility to enter the study within 34 days (Days -35 to -2) prior to dosing on Period 1 Day 1. Replacement subjects will not be enrolled. For all subjects, routine Screening procedures will be performed.

Eligible subjects will be admitted to the study site on the day prior to GDC-9545 dosing (Check-in [Day -1]) of Period 1 to collect baseline data and familiarize the subjects with study procedures that will be used during the rest of the study. On Period 1 Day 1, subjects will be randomly assigned to one of six possible treatment sequences and the first dose of GDC-9545 in the assigned sequence will be administered in the morning. The washout period between doses will be a minimum of 10 days based on the GDC-9545 geometric mean $t_{1/2}$ of approximately 40 hours.

5. SAMPLE SIZE JUSTIFICATION

The sample size chosen for this study was based upon precedent set by other PK studies of similar nature and was not based on power calculations. Eighteen subjects will be enrolled so

7. DEFINITIONS OF POPULATIONS

Any protocol deviations will be considered prior to database lock for their importance and taken into consideration when assigning subjects to populations.

7.1. All Subjects Population

The all subjects population will include all subjects who signed the informed consent form and had any study assessment recorded in the database per the protocol.

7.2. Safety Population

The safety population will consist of all subjects who received at least 1 dose of study drug.

7.3. Pharmacokinetic Population

The PK population will consist of all subjects who received at least 1 dose of study drug and have at least 1 evaluable postdose PK sample. A subject may be excluded from the PK summary statistics and statistical analysis if the subject has an AE of vomiting that occurs within 2 times median t_{max} .

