Potential subjects will be screened to assess their eligibility to enter the study within 34 days (Days -35 to -2) prior to dosing on Period 1 Day 1. Replacement subjects will not be enrolled. For all subjects, routine Screening procedures, as outlined in Section 5.1, will be performed.

Eligible subjects will be admitted to the study site on the day prior to GDC-9545 dosing (Check-in [Day -1]) of Period 1 to collect baseline data and familiarize the subjects with study procedures that will be used during the rest of the study. On Period 1 Day 1, subjects will be randomly assigned to one of six possible treatment sequences and the first dose of GDC-9545 in the assigned sequence will be administered in the morning. The washout period between doses will be a minimum of 10 days based on the GDC-9545 geometric mean apparent terminal elimination half-life ($t_{1/2}$) of approximately 40 hours.

Subjects will be confined at the study site from the time of Check-in (Day -1) until Clinic Discharge on Day 8 of each period. Subjects will return to the study site for a Follow-up visit 12 to 14 days after the last dose of GDC-9545. A detailed list of assessments during confinement is included in [Table 7-1](#).

In this study design, physical examinations, 12-lead ECGs, vital signs, How do you feel? (HDYF?) inquiries, clinical laboratory evaluations ([Appendix A](#)), and PK sampling will be performed at Screening, at specified times during the study, and/or at Follow-up/Early Termination (ET; for specific timepoints and details on each study variable, refer to [Section 7](#)). After informed consent has been obtained but prior to initiation of study drug administration (Period 1 Day 1), only SAEs caused by protocol-mandated interventions will be reported. After initiation of study drug administration on Period 1 Day 1, all AEs, whether volunteered, elicited, or noted upon physical examination, will be recorded throughout the study (i.e., from Period 1 Day 1 until Follow-up/ET). The Sponsor should be notified if the Investigator becomes aware of any SAE that occurs after the follow-up period (defined as 12 to 14 days after the last dose of GDC-9545) if the event is believed to be related to prior study drug treatment.

A schedule of activities is presented in [Table 7-1](#).

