For multiple peaks, the highest postdose concentration will be reported as C_{max} . In the case that multiple peaks are of equal magnitude, the earliest t_{max} will be reported.

8.5.1.1. Criteria for Handling Concentrations Below the Limit of Quantification in Pharmacokinetic Analysis

Concentration values that are below the limit of quantification (BLQ) will be set to zero, with defined exceptions as follows;

- Any embedded BLQ value (between 2 quantifiable concentrations) and BLQ values following the last quantifiable concentration in a profile will be set to missing for the purposes of PK analysis.
- If there are late positive concentration values following 2 BLQ concentration values in the apparent terminal phase, these values will be evaluated. If these values are considered to be anomalous, they will be set to missing.
- If an entire concentration-time profile is BLQ, the profile will be excluded from the PK analysis.
- If a predose concentration is missing, these values may be set to zero.

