8.5.3. Pharmacokinetic Statistical Methodology

All PK concentrations and parameters will be listed.

Descriptive statistics (mean, median, minimum, maximum, SD, geometric mean, and geometric CV) will be calculated for all PK parameters for GDC-9545.

Summary tables, mean (+ SD) figures, overlaying individual figures, and individual figures by treatment and time postdose will be provided for plasma PK concentrations. All figures will be produced on both linear and semi-logarithmic scales. The +SD bars will only be displayed on the linear scale.

Summary tables by treatment will be provided for all PK parameters, with the exception of regression diagnostic PK parameters.

The PK parameters C_{max} , AUC_{0-t} , and $AUC_{0-\infty}$ for GDC-9545 will be analyzed to evaluate the relative bioavailability of GDC-9545 as a Phase 3 capsule formulation compared to a Phase 1 tablet formulation under fasted conditions and to assess the food effect on GDC-9545 PK for a Phase 3 capsule formulation. The mixed-effect analysis of variance model for three-period crossover design will be used for formulation comparison and fasted state and fed state comparison of capsule. The model will include sequence, formulation, and period as fixed effects and a random effect for subject within sequence. An unstructured covariance structure will be used; however, if this fails to converge, an alternative covariance structure may be applied.

Log transformed C_{max} , AUC_{0-t} , and $AUC_{0-\infty}$ values will be evaluated to estimate ratios of geometric mean values and the corresponding 90% confidence intervals (CIs).

The comparisons of interest are:

Relative bioavailability: Treatment B, capsule (Test) vs Treatment A, tablet (Reference)

Food effect on capsule: Treatment C, fed (Test) vs Treatment B, fasted (Reference)

An example of the SAS code that will be used (assuming formulation coding is 1 = Treatment A, 2 = Treatment B and 3 = Treatment C) is as follows:

```
proc mixed data=pk;
  by parcatln parcatl pkday paramn param;
  class trtan aperiod trtseqp usubjid;
  model log_pk = trtan aperiod trtseqp / residual ddfm=kr;
  random intercept / subject=usubjid(trtseqp) type=un;
```

```
estimate `Capsule - tablet' trtan -1 1 0/ cl alpha=0.1;  
estimate `fed - fasted' trtan 0 -1 1/ cl alpha=0.1;  
run;
```

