The parameter t_{max} will be analyzed nonparametrically using the Wilcoxon signed-rank test. The median difference between the test and reference investigational products and the corresponding 90% CI will be calculated.

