8.6. Safety and Tolerability Assessments

8.6.1. Adverse Events

All AEs will be coded using the Medical Dictionary for Regulatory Activities Version 22.1 (or higher if upversioned during the study). All AEs will be assigned severity grade using National Cancer Institute Common Terminology Criteria for Adverse Events Version 5.0 (or higher if upversioned during the study).

A treatment-emergent AE (TEAE) will be defined as an AE that starts during or after the first dose, or starts prior to the first dose and increases in severity after the first dose.

A treatment-related TEAE will be defined as a TEAE with a relationship of related to the study treatment, as determined by the investigator.

The AEs of special interest for this study are defined as follows:

- Cases of potential drug-induced liver injury that include an elevated alanine aminotransferase (ALT) or aspartate aminotransferase (AST) in combination with either an elevated bilirubin or clinical jaundice, as defined by Hy's Law
- Suspected transmission of an infectious agent by the study drug as defined below:
 - ○ Any organism, virus, or infectious particle (eg, prion protein transmitting transmissible spongiform encephalopathy), pathogenic or non-pathogenic, is considered an infectious agent. A transmission of an infectious agent may be suspected from clinical symptoms or laboratory findings that indicate an infection in a subject exposed to a medicinal product. The term applies only when a contamination of the study drug is suspected
- Grade ≥ 3 nausea/vomiting/diarrhea
- Grade ≥ 2 thromboembolic events (pulmonary embolism, deep vein thrombosis, and embolism)
- Grade ≥ 3 renal failure (including acute kidney injury or other similar medical concepts)
- Grade ≥ 3 hepatitis or elevation in ALT or AST
- Grade ≥ 2 vaginal or uterine hemorrhage
- Grade ≥ 2 bradycardia

- Any grade of endometrial cancer.

All AEs, serious AEs and AEs of special interest will be listed. In addition to the data recorded in the database, the listings will include derived onset time and duration. Onset time will be calculated from the time of the last dose for TEAEs only.

The frequency of subjects with TEAEs and the number of TEAEs will be summarized for the following categories:

- TEAEs (overall, serious, leading to discontinuation, and leading to death) by treatment
- TEAEs by severity and treatment
- Treatment-related TEAEs (overall, serious, leading to discontinuation, and leading to death) by treatment

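### The vomiting exclusion in SAP 7.3 removes the subject rather than the affected period, so using it can discard intact profiles from a comparison that vomiting did not touch

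*SAP*

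**What the plan says.** SAP 7.3 defines the PK population by subject (at least one dose and one evaluable postdose sample) and adds: "A subject may be excluded from the PK summary statistics and statistical analysis if the subject has an AE of vomiting" within twice the median tmax. It names no period, treatment or profile. SAP 8.1 then has summaries and analyses use the subjects assigned to the relevant population. The protocol has no vomiting rule; its section 9.4 leaves selection of subjects to the SAP and/or the CSR.

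Elsewhere the SAP works below subject level:

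- In 8.5.1.1, if a profile is entirely below the limit of quantification, "the profile will be excluded from the PK analysis".
- In 8.5.1.3, AUC0-∞ values with at least 30% extrapolation are dropped as values.
- In 8.5.1.4, single anomalous points may be dropped with justification.

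The comparisons in SAP 8.5.3 are B versus A (capsule versus tablet, fasted) and C versus B (fed versus fasted capsule). Both come from one mixed model with a "random effect for subject within sequence". In addition, tmax is "analyzed nonparametrically using the Wilcoxon signed-rank test". On enrolment, Protocol 4.1 states: "Replacement subjects will not be enrolled".

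**The concern.** Vomiting soon after one dose compromises absorption of that dose. It says nothing against profiles from doses given at least 10 days earlier or later. Removing the subject therefore discards two further profiles for each affected one.

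This matters most after A or C. A subject who vomits only after C has intact A and B profiles, which are all that B versus A needs from her. A subject who vomits only after A has intact B and C profiles for C versus B. Under 7.3 as written, either subject can be lost to the comparison that vomiting left alone, in the mixed model and in the paired tmax test. Treatment B enters both comparisons, so after B there is no unaffected comparison, although the intact A and C profiles would still go.

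With 18 subjects and no replacements, this is an avoidable loss of precision. No bias is claimed. No decision threshold is at stake, since the documents set none.

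**Working it through.** The plan gives no figure to reproduce on this point, and its sample size rests on precedent. The check compares the two exclusion units on the SAP's own layout.

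**Inputs from the documents.** Six sequences of 3 subjects (18 subjects, 54 profiles); fixed treatment, period and sequence; random subject intercept; 90% confidence intervals.

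**Assumptions.** Within-subject CV of 15% to 30%; intra-subject correlation of 0.5 and 0.8 for the standard errors in σw units; between-subject variance of 0.06 for the confidence multipliers; one or two subjects vomiting after one treatment only.

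**Step 1: standard error of the unaffected comparison**, in units of the within-subject log SD σw, by generalised least squares:

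- Full data: √(2/18) = 0.333.
- Period-level exclusion, 1 or 2 subjects: 0.333, unchanged, because both treatments in the comparison are still observed in all 18 subjects.
- Subject-level exclusion, 1 subject: 0.3436, ratio 0.3436/0.3333 = 1.031.
- Subject-level exclusion, 2 subjects from different sequences: 0.3542, ratio 1.063. Over random choices of the two subjects the ratio averages about 1.065.

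Simple counting gives nearly the same: √(18/17) = 1.029 and √(18/16) = 1.061; the remainder is lost balance. The ratios hold at both correlations and at every CV tried. They are the same for vomiting after C (B versus A) and after A (C versus B).

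**Step 2: confidence limits.** σw = √ln(1 + CV²); at CV 20% this is √ln(1.04) = 0.198, so the SE is 0.333 × 0.198 = 0.0660 with period-level exclusion. With subject-level exclusion it is 0.0680 for one subject and 0.0703 for two (average over random draws).

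Upper multiplier = exp(t(0.95, df) × SE), with df = profiles − subjects − 4:

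- Period-level: 53 − 18 − 4 = 31 and 52 − 18 − 4 = 30.
- Subject-level: 51 − 17 − 4 = 30 and 48 − 16 − 4 = 28.

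| Assumed CV | Period-level, 1 / 2 subjects | Subject-level, 1 / 2 subjects |
|---|---|---|
| 15% | 1.0880 / 1.0881 | 1.0909 / 1.0943 |
| 20% | 1.1184 / 1.1186 | 1.1224 / 1.1270 |
| 30% | 1.1805 / 1.1807 | 1.1867 / 1.1939 |

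**Step 3: the comparison that is affected.** When vomiting follows B, or for the comparison that uses the affected treatment, subject-level exclusion widens the interval by only about 1% for one subject and 2% for two, relative to period-level exclusion.

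**Step 4: tmax.** The paired test for the unaffected comparison keeps 18 pairs with period-level exclusion and 17 or 16 with subject-level exclusion.

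**Step 5: how often.** The documents give no rate for this setting. Protocol Table 6-1 reports treatment-related vomiting in 2 of 10 patients at 30 mg and in 4% of 74 overall, but these were patients on daily dosing. At assumed per-dose rates of 2% and 4%, the expected number of subjects vomiting in any period is 18 × (1 − 0.98³) = 1.1 and 18 × (1 − 0.96³) = 2.1. These are upper bounds, because not all vomiting falls within the window.

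**The case against.** The sentence permits exclusion and does not require it. A window expressed in multiples of tmax only has meaning relative to a dose, and "Summary tables by treatment will be provided for all PK parameters", apart from regression diagnostics. A pharmacokineticist could therefore read the rule as leaving the subject out only for the treatment after which she vomited, consistent with the lower-level exclusions elsewhere in the SAP. That reading is possible. But the stated unit is the subject, the sentence sits in a population definition, and no other text in the protocol or SAP narrows it. The separate table and listing shells are not available here and might.

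The second objection is size, and it stands. The 3% and 6% apply only to vomiting after A or C. The study has no power target or equivalence bounds, and it already accepts 12 completers, at which the standard error is 0.4082/0.3333 = 1.22 times that of the full design. One or two lost subjects lie well inside that tolerance. The CV and the number of early vomiters are assumptions. This makes the point minor; it does not make the subject the right unit.

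**Conclusion.** The concern holds as a minor, conditional point. As written, SAP 7.3 lets intact profiles be discarded. For one or two subjects who vomit only after A or only after C, the standard error of the unaffected comparison is about 3% or 6% larger than it need be, at any within-subject CV from 15% to 30%. After B the loss is about 1% for one subject. The consequence is precision only, and it is nil if nobody vomits within the window or the option is not used. The calculation assumes otherwise complete data in all 18 subjects and the random-intercept model in SAP 8.5.3.

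**What to change.** Change the unit in SAP 7.3. Suggested wording:

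> When vomiting starts within twice the median tmax after a dose, PK parameters from that treatment period may be left out of the PK summaries and models; the remaining periods of that subject stay in. The median is that of the same treatment in this study, calculated before any such exclusion.

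The last sentence settles a small gap in the same rule: 7.3 does not say which median tmax is meant, and by treatment is the natural reading.

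The cost is SAP wording only. The model accepts a missing period, and SAP 8.6.1 already supplies the timing needed to apply the window: "Onset time will be calculated from the time of the last dose for TEAEs only". Optionally, also show the analysis with all profiles kept. That would add three mixed-model runs (Cmax, AUC0-t, AUC0-∞) and two tmax tests, and only if a period is actually excluded.

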8. STATISTICAL METHODOLOGY

8.1. General

Listings will be provided for all data captured in the database. Listings will include all subjects assigned to the all subjects population and include data up to the point of study completion or discontinuation. Subjects are generally considered to have completed the study if they completed all protocol-specified procedures and assessments for the Follow-up visit. Any subject who discontinued the study will be identified accordingly in the listings. Summaries and statistical analyses will include the subjects assigned to the relevant population based on data type.

Data analysis will be performed using the SAS[®] statistical software package Version 9.4 (or higher if upversioned during the study).

Analysis Data Model (ADaM) datasets will be prepared using Clinical Data Interchange Standards Consortium (CDISC) ADaM Version 2.1 (or higher if upversioned during the study) and CDISC ADaM Implementation Guide Version 1.2 (or higher if upversioned during the study). Pinnacle 21 Community Validator Version 2.2.0 (or higher if upversioned during the study) will be utilized to ensure compliance with CDISC standards.

Caution should be used when interpreting results from the statistical analyses conducted in this study because the sample size is not based on power calculations.

Where reference is made to 'all calculations', this includes, but is not limited to, summary statistics, statistical analyses, baseline derivations, changes from baseline, and any parameter derivations.

8.1.1. Calculation of the Summary Statistics

For continuous data the following rules will be applied:

- Missing values will not be imputed, unless specifically stated otherwise.
- Unrounded data will be used in the calculation of summary statistics.
- If the number of subjects with valid observations (n) < 3 , summary statistics will not be calculated, with the exception of n , minimum, and maximum.
- As Early Termination data is not associated with any scheduled timepoint, it will be excluded from all calculations of summary statistics.

For categorical data the following rules will be applied:

- If the categories of a parameter are ordered (eg, AE severity), all categories between the possible minimum and maximum categories will be included, even if $n = 0$ for a given category. If the categories are not ordered (eg, race), only those categories for which there is at least 1 subject represented will be included.
- Missing values will not be imputed, with the exception of AEs where the ‘worst-case’ approach will be taken (see [Section 8.6.1](#)), or unless specifically stated otherwise. A ‘missing’ category will be included for any parameter for which information is missing. This will ensure that the population size totals are consistent across different parameters.

8.1.2. Triplicate Readings

For ECG data only, where triplicate readings are taken, the mean of triplicate readings will replace the original readings in all calculations.

In case of incomplete triplicate readings (eg, only 2 out of 3 readings were recorded), the mean and/or medians will be calculated based on the number of readings available.

8.1.3. Repeat and Unscheduled Readings

For vital signs and ECG data only, any predose value recorded in addition to the original value or a postdose value recorded within 15 minutes of the original value will be defined as a repeat value; any postdose value recorded more than 15 minutes after the original value will be defined as an unscheduled value. For all other data types (eg, laboratory parameters), any value recorded in addition to the original value will be defined as an unscheduled value.

The original value will be replaced by the last associated repeat value in all calculations.

As unscheduled values are not associated with any scheduled timepoint, they will be excluded from all calculations, with the exception of baseline derivations (see [Section 8.1.4](#)).

